### **5.1.2. Analysis of Adverse Events**

Number and percentage of subjects with at least one particular AE (unsolicited/solicited) will be tabulated. Unsolicited AEs will be summarized by System Organ Class and Preferred Term. Solicited AEs will be summarized by class (local, systemic) and preferred term.

For solicited AEs following tables will be provided: summary, by worst severity grade, grade 3, related (systemic only), time to onset (in days) and duration (in days) for most frequent events and body temperature. Note: Duration for solicited AEs is defined as number of days from the start of the event until resolution of the event. The time to first onset is defined as (date of first onset – reference date + 1). The reference date is the start date of the period.

For unsolicited AEs following tables will be provided: summary table (including SAE, fatal outcome, AESI and discontinuation), all events, most frequent, grade 3, permanent stop of vaccine, related, SAE.

Listings and/or subject narratives will be provided as appropriate, for those subjects who die, discontinue study vaccinations due to an AE, or experience a severe or serious AE.

### **5.1.3. Phase allocation of Unsolicited Adverse Events**

Solicited events are always allocated to the respective Post Dose period.

Solicited AEs from the diary will be added to the ADAM database for unsolicited AEs according to the same principles. This means the same event occurring on different days will be allocated to one row with the start date of the AE being the first date of the event and the end date for the event is the last subsequent day of the event. A change in grade will trigger a new row to be added. The same occurs in case of non-subsequent events (for example grade 1 nausea on day 1, 2 and 3 and also on day 6 and 7, which will be allocated to two rows; the duration of the event is 7 days). For further details related to transforming the on-site assessments and diaries of solicited AEs into analysis format please refer to [Attachment 2](#).

#### **Step 1: Allocation of events to the periods:**

Adverse events in the SDTM database are allocated to periods based on their start date/time. If the start date/time of an event falls between (or on) the start and stop date/time of a period, the AE is attributed to that period (treatment-emergent principle).

- In case of partial start or stop dates (i.e. time and/or day and/or month and/or year missing), the events are allocated to the periods using the available partial information on start and end date; no imputation will be done. If, for instance, the AE start date only month and year are available, these data are compared to the month and year information of the periods. This rule may lead to multiplication of the event as a consequence of its assignment to multiple periods.

- In case of a completely missing start date, the event is allocated to the first active treatment phase (post dose 1 period), except if the end date of the AE falls before the start of the first active treatment phase (post dose 1 period).

- In case of a completely missing end date, the date is imputed by the cut-off date of the analysis for subjects still ongoing in the study, and by the end date of the last period for subjects who discontinued or completed the trial.

## **Step 2: Combination of events:**

Overlapping/consecutive events are defined as events of the same subject with the same preferred term which have at least 1 day overlap or for which the start date of an event is 1 day after the end date of the preceding event. Overlapping/consecutive events may be combined into one AE or not, according to the following rules:

1) If overlapping/consecutive events start in one of the following periods - Screening or post dose extension (i.e. non-active periods) followed by an AE in post-dose period (active period) - they are allocated to their respective periods and are considered as separate events.

2) In case overlapping/consecutive events start within a single period, they are considered as one and the same AE. The individual events which contribute to this AE are retained as individual records in the ADaM database but are assigned the same onset, period, and total duration. All related attributes to the AE/phase/period should also be consistent with the new event.

3) In case overlapping/consecutive events start in both an active period followed by a non active period, they are allocated to the active period only and are considered as one and the same AE. The individual events which contribute to this AE are retained as individual records in the ADaM database but are assigned the same onset, treatment period, and total duration. All related attributes to the AE/phase/period should also be consistent with the new event.

4) In case an active period is followed by another active period, and the overlapping/consecutive events start in both periods, they are allocated to their respective period and are considered as separate AEs. The same rule applies for 2 non-active periods.

### Remarks:

1. Events can only be combined into one and the same AE if their start and stop dates are known.
2. In case the completely missing end date is imputed (for period allocation), this date is also considered as a complete date.
3. Time is not considered when determining overlap of events.

#### **5.1.4. Missing Data**

Missing data will not be imputed. Subjects who do not report an event will be considered as subjects without an event. The analysis of the solicited AEs will include only documented safety data.

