#### **Adverse Events**

AEs will be reported by the subject (or, when appropriate, by a caregiver, surrogate, or the subject's legally acceptable representative). AEs will be followed by the investigator as specified in Section 12, Adverse Event Reporting.

For solicited AEs, the following applies:

- **Solicited Adverse Events**

Information related to solicited events as defined in Section 12.1.1, will be recorded by subjects in a diary for 7 days after each vaccination. Each subject will be provided with a diary and instructions on how to complete the diary (Section 9.1.1). There will be a minimum 30-minute post-vaccination, or a minimum 60-minute post-vaccination assessment of solicited events at the site (according to local approvals). Diary information will be transcribed by the study personnel in the appropriate eCRF pages.

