## 2.3. Analysis Sets

### 2.3.1. Full Analysis Set (FA)

The **Full Analysis (FA) Set** includes all subjects who were randomized and received at least one dose of study vaccine, regardless of the occurrence of protocol deviations. Vaccination assignment will follow the as-treated principle. All safety analyses will be based on the FA set. As a sensitivity analysis, key immunogenicity tables will also be based on the FA set.

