## 5. SAFETY

Safety analyses will be performed on the FA. Continuous variables will be summarized using the following statistics, as appropriate: number of observations, median, quartiles (Q1 and Q3), minimum and maximum. Frequencies and percentages (one decimal place) will be generated for categorical variables. No formal comparisons between groups will be provided.

Two types of safety tables will be shown. In the by regimen layout, safety data will be analyzed by vaccine regimens as designed per protocol; data will be presented by period as well as over the entire regimen. Denominator for the percentages is the number of subjects in the considered population and period for a certain regimen (incidence per 100 subjects/period). In the second, by vaccine, safety data will be presented by the different vaccines used in the study but by considering every vaccination administered as a separate safety episode. Denominator for the percentages is the number of vaccinations administered of a certain vaccine (rate per 100 vaccinations of a particular vaccine).

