### 5.1. Adverse Events (AE)

#### 5.1.1. Definitions

Solicited AEs shown in the tables are extracted from the diary pages of the CRF. For unsolicited AEs, only the AEs starting (grade and/or relation) within the 28-day period following each vaccination will be presented in the safety tables except for SAE, which will be captured and tabulated in the outputs covering the whole study period. All other collected unsolicited adverse events will be presented through listings.

Solicited local AEs will be by definition considered as related to the study vaccine.

The severity of the AEs will be classified as grade 1 to 4. Solicited events that are graded less than grade 1, are not considered as AE. In case no grades are available, the grading of the solicited events will occur according to the grading list in [Attachment 1](#).

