**Attachment 3: Transforming the on-site assessments and diaries of solicited AEs into analysis format**

When creating the analysis dataset for solicited AEs, solicited AEs (recorded by day on the SR and FA domains) need to be converted into the same format as unsolicited AEs (recorded by event). For this purpose, the start date of the AE will be considered as the date of first occurrence of the solicited AE. If on subsequent day(s), the same grade is reported, the last reported date is used as the end date of the AE. A new record is created in case the grade of the event changes. If there is a time gap of at least one day between two (or more) occurrences of the same solicited AE, then the second (and/or next) occurrence will be considered as a new AE. In case no data is reported for a day, this is analyzed as no event reported. If the on-site assessment differs in grade or relatedness with the Day 1 diary data, the on-site assessment should be recorded as a separate record in the database.

The example below shows how the solicited AE should be converted into a format of unsolicited AEs:

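### Solicited adverse event rates count vaccinated subjects with no diary as event-free, and the SAP's rule for events separated by a gap contradicts its own worked example

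*SAP*

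**What the plan says.** **Denominator.** SAP 2.3.1 fixes the population: "All safety analyses will be based on the FA set". SAP 5 then defines the by-regimen percentages: "Denominator for the percentages is the number of subjects in the considered population and period for a certain regimen". On the source of the numerator, SAP 5.1.1 says: "Solicited AEs shown in the tables are extracted from the diary pages of the CRF". SAP 5.1.4 handles absence of a report: "Subjects who do not report an event will be considered as subjects without an event". Attachment 3 applies the same idea to a single day: "In case no data is reported for a day, this is analyzed as no event reported". The last sentence of SAP 5.1.4 points elsewhere: "The analysis of the solicited AEs will include only documented safety data".

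**On-site records.** Protocol 9.2.3 plans an observation after every vaccination: "There will be a minimum 30-minute post-vaccination, or a minimum 60-minute post-vaccination assessment of solicited events at the site". Where the on-site grade or relatedness differs from the Day 1 diary, Attachment 3 says "the on-site assessment should be recorded as a separate record in the database". For temperature, SAP 5.3 states that diary and on-site maxima are tabulated separately. Nothing equivalent is said for the other solicited events.

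**Event identity and duration.** The text of Attachment 3 treats a recurrence after a gap of at least one day as a new AE. Its headache example puts records on both sides of a Grade 0 day under one AE identifier with a duration of 6 days, and adds that duration runs from first to last day whatever happens in between. SAP 5.1.3 likewise gives 7 days for nausea on Days 1 to 3 and 6 to 7. The combination rule in that same section joins only events that overlap or start the day after the previous one ends. SAP 5.1.2 measures duration from start to resolution. SAP 5.1.3 also refers the reader to Attachment 2 for the diary conversion, which is in Attachment 3.

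**The concern.** Solicited events are a primary endpoint (Protocol 2.1.2), to be reported by frequency, severity and duration (Protocol 11.7). Safety is descriptive with no testing, so the printed percentage is itself the result. In arms of 24 and 12, one or two subjects move it visibly.

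Taken together, the denominator provisions turn a missing diary into a favourable observation. The error has one direction: a subject whose diary is absent can add to the denominator but not to the diary-based numerator. The closing sentence of SAP 5.1.4 could lead another programmer to drop such subjects and print a different rate. What counts as documented matters too. If the on-site check qualifies, almost nobody is excluded under that sentence, and 30 to 60 minutes of observation stands in for 7 days of diary.

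On identity and duration, two programmers could each follow part of the SAP and produce different event counts and different duration tables from the same diaries.

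**Working it through.** **Part 1: effect of missing diaries**

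Inputs:
- n = 24 active and 12 placebo toddlers (Protocol 3.1, Table 5). SAP Table 1 still shows 32 and 16, although the text of SAP 1.2 gives 36 in total; the protocol figures are used here.
- k = subjects in the arm with no diary in the period. Not given; 1 and 2 are assumed.
- p = event rate among subjects with a diary. Not given; 20%, 50% and 80% are assumed.

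The number with an event is x = p(n − k). The diary-based rate is x/(n − k) = p. The all-subject rate is x/n = p(n − k)/n. The loss is p − p(n − k)/n = pk/n. In percentage points:

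| n | k | p = 20% | p = 50% | p = 80% |
|---|---|---|---|---|
| 24 | 1 | 0.8 | 2.1 | 3.3 |
| 24 | 2 | 1.7 | 4.2 | 6.7 |
| 12 | 1 | 1.7 | 4.2 | 6.7 |
| 12 | 2 | 3.3 | 8.3 | 13.3 |

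Check with whole subjects:
- n = 24, 22 diaries, 11 with the event: 11/24 = 45.8% against 11/22 = 50.0%, a loss of 4.2 points.
- n = 12, 10 diaries, 5 with the event: 5/12 = 41.7% against 5/10 = 50.0%, a loss of 8.3 points.

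In the first case, if one of the two subjects without a diary had an on-site event and on-site records were tabulated, the all-subject figure would be 12/24 = 50.0%. The role of on-site records therefore has to be settled together with the denominator.

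**Part 2: event identity and duration**

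The plan's own figures reproduce under its first-to-last-day rule, duration = last day − first day + 1:
- Headache, graded above 0 on Days 1, 2, 4, 5 and 6: 6 − 1 + 1 = 6 days, as stated in Attachment 3.
- Nausea, Days 1 to 3 and 6 to 7: 7 − 1 + 1 = 7 days, as stated in SAP 5.1.3.

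Now apply the gap rule in the text of Attachment 3:
- Headache: Day 3 is Grade 0, so there are two AEs, Days 1 to 2 (2 days) and Days 4 to 6 (3 days).
- Nausea: Days 4 and 5 are clear, so there are two AEs, Days 1 to 3 (3 days) and Days 6 to 7 (2 days).

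The combination rule in SAP 5.1.3 does not rejoin them. The second headache episode starts two days after the first ends (Day 2 to Day 4) and the second nausea episode three days after (Day 3 to Day 6); the rule needs overlap or a one-day step.

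In each example the event count goes from 1 to 2, and the longest single duration falls from 6 or 7 days to 3. SAP 5.1.2 counts subjects with at least one event and their worst grade, so those outputs are the same either way.

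**The case against.** The best case for the SAP on the denominator is that it is settled. SAP 5 defines it, SAP 2.3.1 names the population, and the last sentence of 5.1.4 can be read as a statement about which data are used, not about who is counted. That stands. A reader might infer that the SAP leaves the denominator wholly open; it does not, and the last sentence of 5.1.4 only blurs it. But a clear rule that scores absent diaries as event-free still understates the rate.

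The effect is also probably small. Staff train subjects on the diary (Protocol 9.1.1), there are telephone diary checks, and a diary reviewed early is returned at the next visit (Protocol 9.1.4.2.2 and 9.1.4.2.3). The data presentation specifications, not available here, may already tabulate missing diaries.

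On duration, Attachment 3 gives an explicit first-to-last rule with an example, and the SAP 5.1.3 example agrees, so a programmer has something usable. That stands for duration, but not for event identity. The new-AE statement is hard to read as meaning only a new row, because the same attachment speaks separately of a new record when the grade changes.

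Two further inferences go too far. SAP 5.1.2 does not plainly contradict the examples: measuring to resolution fits them if final resolution is meant. Nor do SAP 5.1.1 and Attachment 3 necessarily conflict over on-site records, since one speaks of tables and the other of the database; a record can be stored without being tabulated. In the headache example, the worst grade is 3 with or without the on-site Grade 2.

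**Conclusion.** Two defects hold.

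First, the SAP's rules taken together keep a Full Analysis subject with no diary in the denominator as event-free. Missing diaries can only lower a solicited-event rate or leave it unchanged. The loss is pk/n, which gives the ranges tabulated above. These rest entirely on assumed k and p; with no missing diaries there is no loss.

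Second, Attachment 3 contradicts itself on whether a gap starts a new AE. The combination rule in SAP 5.1.3 sides with splitting, and the two worked examples side with joining. Event counts and duration tables depend on the answer.

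No decision rule changes, because no formal testing of safety data is planned. The documents do not show that any reported rate is wrong. They show that the rules can understate a primary endpoint and leave one of its outputs undetermined. That is worth correcting, and confidence in its practical weight is moderate.

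**What to change.** 1. State one denominator rule in SAP 5.1.4. For each post-dose period, give the solicited-event rate among Full Analysis subjects with documented solicited data in that period, and define documented as diary only or diary plus on-site. Print the all-subject rate of SAP 5 alongside, so that the planned basis is kept and an on-site event in a subject without a diary is not lost. Show, by arm, the number of subjects with no diary and with a partial diary. The partial count is needed because blank days in those diaries still count as no event under Attachment 3.
2. Adopt one AE identifier and duration rule across SAP 5.1.2, 5.1.3 (both the nausea example and the combination rule) and Attachment 3 (both text and example). Say in 5.1.2 whether resolution means final resolution. If the first-to-last-day measure is kept, label it as a span.
3. State whether on-site records for solicited events other than temperature are tabulated or only stored. Correct the reference in SAP 5.1.3 from Attachment 2 to Attachment 3.

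The cost is SAP wording and a few extra table rows. No new data collection is needed.

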#### **5.1.5. Solicited Local (Injection Site) Reactions**

The analysis of local solicited adverse events, for all subjects will include:

- Erythema
- Induration/swelling
- Pain/tenderness

#### **5.1.6. Solicited Systemic Adverse Events**

The analysis of systemic solicited adverse events for adult subjects will include:

- Fatigue
- Headache
- Myalgia
- Arthralgia
- Chills
- Nausea
- Fever (ie, body temperature  $\geq 38$  °C)

The analysis of systemic solicited adverse events for pediatric subjects will include:

- Loss of appetite
- Vomiting
- Diarrhea
- Decreased activity/lethargy
- irritability/crying
- Fever (ie, body temperature  $\geq 38$  °C)

### **5.2. Clinical Laboratory Tests**

For laboratory safety parameters, only abnormalities emerging after vaccination will be tabulated by worst abnormality grade using the FDA table in [Attachment 1](#).

An abnormality (toxicity grade or abnormality based on normal ranges) will be considered as emerging in a particular period if it is worse than the baseline value. If the baseline is missing, the abnormality is always considered emerging. A shift from ‘abnormally low’ at baseline to ‘abnormally high’ post baseline (or vice versa) is also emerging. In case a laboratory test result is censored (no numeric value is available, but only a verbatim term) then a numeric value will be imputed by a value exceeding the cut-off value with one unit. (<x: subtract 1 unit from x, >x: add 1 unit to x; <3.45 is imputed with 3.44).

In case no toxicity grades are defined for a test, the abnormalities (above/below normal range) will be used. In determining toxicity grades, the following rules are applied:

- worst grades/abnormalities are determined over the whole observational period for each trial period separately, including all post-baseline measurements of that period.
- The abnormalities ‘abnormally low’ and ‘abnormally high’ are considered equally important, i.e. if a subject has as well an abnormally low as an abnormally high value post-baseline, both abnormalities are shown in the tables. (This means that the sum of the percentages can be more than 100%)
- Note: as the grading scale for some parameters in the grading table has some gaps (zones where no toxicity grade definition exists), laboratory results falling in these zones will be allocated to the adjacent worst-case grade.
- If a lab value falls within the grading as specified in the grading table but also within the local lab normal limits, the value is considered as normal.

For the grades, no distinction will be made between test results of samples obtained under fasting and under non-fasting conditions: in case limits under fasting and non-fasting conditions differ, the limits of the conditions (fasting/non-fasting) of scheduled visits as planned in the CTP will always be used, also for samples obtained under a different condition (e.g. samples of withdrawal visits).

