**TIME AND EVENTS SCHEDULE – COHORT 1: SEROPOSITIVE TODDLERS**

Phase	Screening	Active									Safety FU a	
		1	2	3	4	5	6	7	8	9 b		Exit d
Clinic Visit #	1											During both the active and safety FU phases: FU outside RSV season at 30-day intervals; FU in season at 14-day intervals
Visit Timing		Vac 1	Vac 1 + 3 d	Vac 1 + 7 d	Vac 2	Vac 2 + 3 d	Vac 2 + 7 d	Vac 2 + 28 d	Vac 2 + 6 mo			
Visit Week		0		1	4		5	8	30			
Target Visit Day ±window	-42 to 1	1	4±1 f	8±2 g	29±3	32±1 f	36±2	57±3	211±14			
Visit Type	Screening	VACCINE 1	Safety (Telephone)	Safety	VACCINE 2	Safety (Telephone)	Safety	Safety and Immuno.	Safety and Immuno.	Early Exit	Safety FU (Telephone)	
Subject diary distribution v		●			●							
Subject diary review			Ⓢ	●		Ⓢ	●					
Approx. daily blood draw, mL	5.5	–	–	5.0	–	–	2.0	2.0	5.0	–	–	
Approx. cumulative blood draw, mL	5.5	5.5	5.5	10.5	10.5	10.5	12.5	14.5	–	–	–	

① pre-dose; ② abbreviated physical examination only at the discretion of the investigator (based on health status of subject); ③ pre- and post-dose; ④ baseline immunogenicity blood draw can take place *either* at screening *or* prior to vaccination on Day 1, at the discretion of the investigator; ⑤ if at least 14 days after the previous blood draw for immunogenicity; ⑥ if within 7 days of the previous vaccination; ⑦ if within 28 days of the last vaccination; ⑧ check of diary during the telephone call; ⑨ laboratory tests at screening are to be done within 28 days of randomization; ⑩ at the discretion of the investigator (based on health status of subject); ⑪ If before Day 29 collect 4 mL cellular + 1 mL humoral; if after Day 29 collect 2 mL humoral only.

- Safety follow-up during both the active and safety follow-up phases through 1 year after the first dose: telephone call (or clinic visit) to parent(s)/legal guardian(s) of Cohort 1 subjects– every 30 days ± 7 days outside the RSV season, but every 14 days ± 3 days in season. Final Telephone call 1 year post-first dose will be at Day 365 ± 14 days.
- If Visit 9 occurs during the RSV season, an additional visit will be made by telephone at the end of the RSV season to collect safety information
- For those subjects who are unable to continue participation in the study up to Visit 8, but for whom consent is not withdrawn, an exit visit will be conducted as soon as possible

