#### **9.1.3.2.5. Early Withdrawal – Early Exit Visit**

For those subjects who are unable to continue participation in the study, but who do not withdraw consent, an early exit visit will be conducted as soon as possible. In the event of early withdrawal from the study, all procedures required at the final visit (Section 9.1.3.2.4) will be performed. Samples for safety laboratory testing (hematology and biochemistry) will only be collected if the early exit is within 7 days of the first vaccination. Samples for immunogenicity assessments will only be collected if the early exit is at least 14 days after the previous blood draw for immunogenicity. A nasal turbinate sample for immunogenicity assessment will be collected if the early exit is within 14 days of the previous vaccination.

If the early exit visit occurs within 7 days of the last vaccination, solicited AEs will be recorded; if the early exit visit occurs within 28 days of the last vaccination, unsolicited AEs will be recorded.

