### 9.2.3.2. Clinical Laboratory Tests – Cohort 0 Only

Blood samples for serum chemistry and hematology will be collected at screening, pre-vaccination on Day 1 and on Day 8. The following tests will be performed by a local laboratory (\*parameters only measured at screening):

- **Hematology Panel**
  - hemoglobin
  - white blood cell (WBC) count with differential
  - platelet count
  - prothrombin time\*
  - activated partial thromboplastin time\*
  - fibrinogen\*

---

a Persistent (>48 hours) clinical symptoms of rhinitis (sneezing or runny nose or congestion) and persistence (>24 hours) of one or more of the following: cough, abnormal breathing, fever, lethargy or decreased appetite.

- **Biochemistry Panel**

- sodium
- potassium
- creatinine
- blood urea nitrogen
- aspartate aminotransferase (AST)
- alanine aminotransferase (ALT)

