***Repeat of Clinically Significant Laboratory Tests***

For any clinically significant abnormal laboratory value that has increased in grade over baseline, the test must be repeated at the next scheduled visit or sooner based on the investigator’s judgment, however Grade 3 abnormalities should be retested within 48 hours. Any clinically significant abnormalities (including those persisting at the end of the study or at early withdrawal) will be followed by the investigator until resolution or until a clinically stable endpoint is reached (see Section [12.3](#)).

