#### **11.10. Study Vaccination Pausing Rules**

The PIs and the SRP will monitor the study vaccination pausing rules. If study vaccination is considered to raise significant safety concerns, further vaccination of subjects will be suspended until IDMC review is carried out and subsequent communication between the sponsor and the investigators takes place.

The occurrence of any of the following events will lead to suspension of further study vaccination, and trigger a meeting of the IDMC to discuss study suspension, adaptation or discontinuation of further vaccination:

1. One or more subjects in the same cohort experience an SAE or other potentially life-threatening (Grade 4) event that is determined to be related to study vaccine; *OR*
2. One or more subjects in the same cohort experience anaphylaxis clearly not attributable to other causes than vaccination with study vaccine; *OR*
3. Two or more subjects in the same cohort experience a Grade 3 or 4 unsolicited AE of the same type, determined to be related to study vaccine, that persists for 72 hours or longer; *OR*
4. Two or more subjects in the same cohort experience a Grade 3 or 4 solicited systemic AE of the same type, determined to be related to study vaccine, that persists for 72 hours or longer; *OR*
5. Two or more subjects in Cohort 0 experience a persistent (upon repeat testing) Grade 3 or 4 laboratory abnormality related to the same laboratory parameter and considered related to study vaccine, that persists for 72 hours or longer; *OR*

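### No adult safety laboratory sample is scheduled after dose 2, but the SAP tabulates laboratory abnormalities by post-dose period with denominators that do not depend on who was tested

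*SAP*

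**What the plan says.** **Sampling.** Protocol 9.2.3.2 states: "Blood samples for serum chemistry and hematology will be collected at screening, pre-vaccination on Day 1 and on Day 8". PT, aPTT and fibrinogen are taken at screening only. The Cohort 0 Time and Events Schedule agrees, and the descriptions of Visits 5 to 8 (Protocol 9.1.3.2.1, 9.1.3.2.3 and 9.1.3.2.4) list no safety laboratory sample. Protocol 3.1 fits this design: laboratory data enter the Cohort 0 7-day review after the first dose, while the second-dose review names only adverse events.

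**Tabulation.** SAP Table 2 makes Post-dose 2 a period of its own, starting at the second vaccination. SAP 5.2 says that "worst grades/abnormalities are determined over the whole observational period for each trial period separately, including all post-baseline measurements of that period".

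**Denominators.** SAP 5, which heads all the safety subsections, describes two layouts. For by-regimen tables: "Denominator for the percentages is the number of subjects in the considered population and period for a certain regimen". For by-vaccine tables: "Denominator for the percentages is the number of vaccinations administered of a certain vaccine". SAP 5.2 adds no laboratory-specific denominator, does not restrict the tables to dose 1, and does not mention that the second period is unsampled.

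**Layout.** Protocol 11.7 analyzes safety by regimen. SAP 1.6, which lists changes to the planned analyses, covers only interim analyses and the related IDMC unblinding. It does not mention a by-vaccine layout.

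**Early exit.** Protocol 9.1.3.2.5 says: "Samples for safety laboratory testing (hematology and biochemistry) will only be collected if the early exit is within 7 days of the first vaccination". The schedule's marker for the same sample reads, as extracted, "if within 7 days of the previous vaccination". The key to that marker is printed under the Cohort 1 table and serves both cohorts.

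**The concern.** A laboratory percentage can be read only if the people in the denominator had a chance to be found abnormal. After dose 2 no adult has a scheduled chance. A zero there looks like a safety result when it is an absence of data. Next to a non-zero dose 1 column it would suggest that laboratory tolerability improves with the second dose, purely because testing stopped.

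The per-vaccination layout has the same fault in another form. Second vaccinations would enter the denominator but could add almost nothing to the numerator, so the rate falls for reasons unrelated to the vaccine.

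The first primary objective is the safety and tolerability of a two-dose regimen in adults. A table that appears to cover both doses but has data for one invites a broader statement than the trial can support.

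**Working it through.** **1. Is there really no laboratory draw after Day 8?** The protocol gives a total of about 295 mL per Cohort 0 subject (9.1.1). Adding up the schedule:

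| Visit | Safety lab / serology (mL) | Immunogenicity (mL) | Visit total | Cumulative |
|---|---|---|---|---|
| Screening | 10 + 15 | – | 25 | 25 |
| Day 1 | 5 | 40 + 40 | 85 | 110 |
| Day 8 | 5 | – | 5 | 115 |
| Day 29 | – | 40 + 40 | 80 | 195 |
| Day 36 | – | – | 0 | 195 |
| Day 57 | – | 40 + 10 | 50 | 245 |
| Day 211 | – | 40 + 10 | 50 | 295 |

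The stated 295 mL is reproduced exactly with no safety laboratory blood after Day 8. One further 5 mL draw would make it 300 mL. Planned post-vaccination laboratory coverage is therefore 12/12 adults after dose 1 and 0/12 after dose 2.

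**2. The SAP denominators applied literally.** Inputs: 8 active and 4 placebo adults (Table 1), both doses given, no unscheduled samples. Let k be the number in an arm with an emerging abnormality after dose 1. For n subjects in the arm:

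- Post-dose 1: k/n
- Post-dose 2: 0/n, whatever the true rate
- by vaccine: k/(2n)
- entire regimen: k/n

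| Arm | k | Post-dose 1 | Post-dose 2 | By vaccine |
|---|---|---|---|---|
| Active, n = 8 | 1 | 1/8 = 12.5% | 0/8 = 0.0% | 1/16 = 6.25% |
| Active, n = 8 | 2 | 2/8 = 25.0% | 0/8 = 0.0% | 2/16 = 12.5% |
| Active, n = 8 | 3 | 3/8 = 37.5% | 0/8 = 0.0% | 3/16 = 18.75% |
| Placebo, n = 4 | 1 | 1/4 = 25.0% | 0/4 = 0.0% | 1/8 = 12.5% |

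The entire-regimen figure equals the Post-dose 1 figure, so it is not diluted.

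**3. Sensitivity to missed second doses.** If m active adults miss dose 2, the by-vaccine rate is k/(16 − m). Its ratio to k/8 is 8/(16 − m): 0.50 for m = 0, 0.53 for m = 1, 0.57 for m = 2 and 0.62 for m = 3. The exact half holds only when everyone receives both doses.

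**4. What a genuine zero would be worth.** Had all 8 active adults been tested after dose 2 with none abnormal, the exact two-sided 95% upper limit would be 1 − 0.025^(1/8) = 36.9%. With nobody tested there is no upper limit to quote, yet the printed cell would look the same.

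**5. With tested-subject denominators.** Post-dose 1 stays k/8 and k/4. Post-dose 2 has 0 tested and shows no percentage. Per tested vaccination the active rate is k/8.

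**The case against.** The strongest reply is that the SAP does not actually order these misleading cells. SAP 5.2 speaks only of periods and never of vaccinations. The by-vaccine layout sits in the general paragraph of SAP 5, whose wording about safety episodes suits adverse events. SAP 1 leaves the list of tables to a separate data presentation document. In addition, 5.2 builds worst grades from measurements. It does not say that unmeasured subjects count as normal; the rule treating non-reporters as event-free is in 5.1.4, on adverse events. An empty or omitted Post-dose 2 table is quite possible. This part stands: both the 0/8 and the k/16 are what the written rules give when applied literally, not results the SAP commits to.

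Nor is the second period certain to be empty. For a clinically significant value that has risen in grade, "the test must be repeated at the next scheduled visit or sooner", and the schedule's version of the early-exit rule could admit a sample after dose 2. This also stands, but such results would be few and selected, which is a reason to count only tested subjects.

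Three stronger inferences are tempting and not supported:

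- A reader might infer that a primary endpoint is compromised. The listed primary endpoints are solicited events, unsolicited events and SAEs. Laboratory grades are not among them, and clinically significant values needing follow-up within 28 days after vaccination are captured as adverse events (Protocol 9.2.3.2).
- A reader might infer that the entire-regimen rate is understated. It is k/8, so only its label can mislead.
- A reader might extend the point to the laboratory pausing rule ("Two or more subjects in Cohort 0 experience a persistent (upon repeat testing) Grade 3 or 4 laboratory abnormality"). The investigators and the study responsible physician monitor that rule during the trial, not from SAP tables. How often blood is sampled is a separate matter from denominators.

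What the reply does not remove is that the only denominators the SAP states ignore testing, although the SAP describes itself as containing everything needed for the safety analysis.

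**Conclusion.** The point holds as a mismatch between the sampling schedule and the stated denominators, limited to Cohort 0 laboratory tables. If all 12 adults receive both doses, no unscheduled or early-exit sample falls after dose 2, and the SAP 5 denominators are used as written, then Post-dose 2 reads 0/8 and 0/4 with no tests behind it. Under the same conditions, any by-vaccine laboratory table halves the active rate, from k/8 to k/16.

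The by-period part rests on explicit text in SAP 5.2. The by-vaccine part is weaker: it rests on the general SAP 5 text and on a table list not available here, so it should not be read as a specified output. Separately, that layout departs from the protocol's by-regimen analysis and is not recorded in SAP 1.6.

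The consequence is moderate: 12 adults, descriptive analysis and no hypothesis test. The risk is a misleading safety table that is cheap to prevent.

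**What to change.** In SAP 5.2:

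- Set the laboratory denominator to subjects with at least one post-baseline result for that parameter in that period. This also handles the coagulation tests, which have no scheduled post-baseline value.
- Show Post-dose 2 as not assessed (no scheduled samples), and list any unscheduled or early-exit results individually.
- Exclude laboratory data from the by-vaccine layout, or drop that layout to match Protocol 11.7. If it is kept for other safety data, record it in SAP 1.6.
- If an entire-regimen laboratory table is kept, footnote that it reflects sampling after dose 1 only.
- State that the laboratory safety conclusion covers dose 1.

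In the protocol, Section 9.1.3.2.5 and the schedule's early-exit marker must be reconciled, since one refers to the first vaccination and the other to the previous one. Check the marker against the original page first, because circled numbers may have been misread in the extracted table.

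The cost is a few lines in the SAP and its table specifications, plus the protocol clarification. This analysis change needs no extra blood and no extra visits. The downside is a slightly narrower laboratory safety statement, which is all the sampling supports.
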